4. SUBJECT SELECTION CRITERIA

The study will enroll 50 to 80 patients presenting to the emergency department following suspected syncope. Patients eligible for enrollment must meet all of the inclusion criteria and none of the exclusion criteria prior to ED discharge:

Inclusion Criteria are as follows:

- 1) Age ≥ 18
- 2) Experienced a syncopal event within the past 48 hours
- 3) Either one of the following profiles apply:
 - a) ED workup indicates that the patient may have experienced syncope that is cardiac in nature (any one or more of the following apply)
 - History or diagnosis of structural heart disease
 - History of cardiovascular disease
 - Age ≥ 40
 - Palpitations experienced pre-syncope
 - Major ECG abnormalities:
 - QRS duration greater than 140 ms
 - PR interval greater than 200 ms
 - Non-specific repolarization abnormality
 - Syncope experienced without any warning

- Syncope experienced while supine
 - Syncope during exercise
- b) ED workup does not indicate a clear cause of the syncopal event

Exclusion criteria are as follows:

- 1) Clear diagnosis of non-cardiac syncope (e.g. orthostatic hypotensive syncope, vasovagal syncope, carotid sinus syncope, situational fainting)
- 2) An active implantable cardioverter-defibrillator (ICD)
- 3) An active unipolar pacemaker
- 4) Significant risk or suffering a cardiovascular event such as:
 - Symptoms of NYHA class III or IV heart failure
 - ED diagnosis of acute coronary syndrome
 - Having required resuscitation in response to the index syncopal event
- 5) Advanced directive prohibiting resuscitation (DNR)
- 6) Physical or mental conditions preventing subjects from interacting with or wearing the device as determined by the investigating physician.
- 7) Bandages or other clinical condition preventing SWD 1000 use
- 8) Injuries or other conditions beyond simple syncope that require hospitalization
- 9) Travel out of town during the study participation period that prevents the field service representative from visiting the subject daily
- 10) Unable or unwilling to provide written informed consent

5. INVESTIGATIONAL PROCEDURE

At the beginning of the study, a ZOLL representative will train a site coordinator and designated ED staff in SWD 1000 use per the Clinician Manual. A training sheet will be used to document that device training was provided by ZOLL to the site coordinator and designated staff.

5.1 Pre-study Assessment

The subject's eligibility to enter the study will be determined during the pre-study assessment. This assessment is to be performed prior to ED discharge. The pre-study assessment will include:

- Reviewing the subject's medical history and symptoms to determine whether the inclusion and exclusion criteria are met using the enrollment questionnaire.
- Discussing the risks and benefits of the study with the subject.
- Obtaining informed consent.

5.2 SWD 1000 Device Setup

Each subject enrolled in the study will be assigned the following:

- one monitor
- one electrode cable
- Replacement electrodes
- two batteries (one battery will power the monitor while the other is being charged)
- one base station (battery charger)
- one patient manual

The monitor will be programmed in accordance with the instructions in the Clinician Manual, section 3, by the ED staff member. The following default settings will be used:

- The energy level for defibrillation will be set to 150 joules for all shocks.
- The rate at which VT is detected will be programmed to 150 BPM
- The rate at which VF is detected will be programmed to 200 BPM.

5.3 SWD 1000 Application

Application and training must occur prior to the subject leaving the hospital.

Once the SWD 1000 monitor is set up, the subject's skin will be prepared in the usual manner for the application of adhesive electrodes, and the electrodes will be applied in the locations described in the Clinician Manual, section 3 by the ED staff.

The ED staff member will then connect the electrode leads to the SWD 1000 electrode belt and allow the monitor to perform a baseline ECG as described in sections 3 and 1 of the Clinician Manual, respectively.

5.4 Subject Training

The ED staff member will provide the subject instructions for the care and use of the SWD 1000, as described in section 4 of the Clinician Manual and section 3 of the Patient Manual. Specific training tasks are as follows:

- The subject will be trained on normal daily maintenance of the device, including the battery change and startup sequences.
- The subject will be trained to respond to alerts and alarms provided by the monitor, including the event detection alarm sequence.
- The subject will be trained to inspect the integrity of the adhesive electrodes and to self-remove and apply replacement electrodes in the event that they fail to adhere.
- The subject will be trained to monitor for and respond to alarms indicating that electrodes have failed to make adequate contact.

- The subject will be trained to initiate manually-flagged ECG recordings in response to certain symptoms, as described in further detail below.

5.5 SWD 1000 Use

The subject will wear the SWD 1000 continuously for the duration of the monitoring period, up to 14 days, unless one of the following conditions applies:

- The subject's index syncopal event has been determined to not be cardiac in nature.
- The subject's condition changes such that an exclusion criterion applies.
- The subject experiences an excessive amount of electrode noise that prevents effective monitoring by the SWD 1000.
- The subject decides to withdraw from the study.

The subject will wear the SWD 1000 continuously except:

- While showering (during which the patient may continue to wear the adhesive electrodes but not the monitor).
- While undergoing a medical procedure that requires SWD 1000 removal (e.g., MRI requires the removal of all metallic objects).

Subjects will not be limited in their daily activities except for being instructed to avoid fully submerging the electrodes in water, such as during bathing or swimming. Subjects are still permitted to shower with the electrodes attached as long as the electrodes are disconnected from the monitor. The subjects will be responsible for charging and exchanging the batteries every 24 hours.

Once the subject is discharged, a properly trained field service representative will be responsible for visiting the patient daily. This representative will be responsible for inspecting the integrity of the electrodes and exchanging them as needed.

Subjects may experience symptomatic events that will help their physician discern a specific cause of the original syncopal event. Symptoms may include dyspnea, lightheadedness or dizziness, or in more serious cases loss of consciousness or chest pain. In such scenarios, subjects will be trained how to initiate a manually-flagged ECG recording when possible so that physician may review the associated ECG and attempt to determine if the event was cardiac in nature. During such an event, subjects are instructed to perform the following steps as described in section 3 of the Patient Manual:

- Hold the SWD 1000 response buttons as described in the patient manual to create a data event flag. This enables the electrocardiographic activity associated with the event to be saved for review

5.6 Response to Cardiac Arrest

It is possible, but not expected, that one or more subjects may experience a spontaneous ventricular arrhythmia. In the event that this does occur, the SWD 1000 alarms that an event has been detected. If this occurs and the subject is conscious, they are instructed to press the device's response buttons to delay shock as described in section 4 of the Patient Manual. The subject's interaction with the device will be logged by the device and can be analyzed

retrospectively. As this is dependent upon the occurrence of a highly unpredictable event (sustained VT/VF, or asystole / near-asystole), studying the subject and device response to such an event is not an end point of the initial stage of this study.

5.7 Subject Monitoring Frequency

The subject and the SWD 1000 device will be evaluated by a trained field service representative within one day of enrollment in the study. Follow-up visits will continue to be performed on a daily basis until the patient monitoring period is complete. During each field service visit, the integrity of the adhesive electrodes will be evaluated for falloff as described in the report form.

6. EVALUATION OF RESULTS

6.1 Data Collection

6.1.1 Observational Data

Throughout the study, observational data will be collected to evaluate care provided to subjects on an outpatient basis. During the daily visits, the field service representative will be tasked with logging any follow up physician appointments ordered for and / or attended by the subject, as well as any return to the ED and / or hospital admission. In addition to the daily logging of said data, an exit evaluation will be conducted 30 days after study enrollment to capture information related to additional follow up care received by the subject after the active participation period. The evaluation will be conducted by study coordinators who will determine where the patient received follow-up care and obtain the appropriate release of records.

6.1.2 Device-Collected Data

While the SWD 1000 is in use by the subject, the monitor will collect and store ECG data, device performance data, and subject-device interaction data. These data can be used to evaluate the subject's ability to interact with the device and to evaluate device performance as needed within the context of this study. Specific data collected by the device are as follows.

- ECG Data
 - All automatically recorded arrhythmic events
 - All subject-initiated ECG recordings
- Device Performance Data
 - ECG signal quality, defined using electrode falloff and signal noise detected by the monitor
 - Therapy electrode preparedness, defined using subject-electrode impedance detected by the monitor
 - Arrhythmia detection and treatment sequence markers
 - Device measurements made during treatment sequences
 - Alarm timing in response to detected arrhythmia

- Transthoracic impedance
- Treatment energy delivered
- Subject-Device Interaction Data
 - Subject compliance (measured as the duration of time the SWD 1000 was powered and being worn).
 - Use of the response buttons during treatment sequences
 - Power cycling (indicative of battery replacement)

Data stored within the monitor will be downloaded to the data-enabled battery charger automatically when within Bluetooth radio range of the charger. Data stored in the charger can then be automatically upload to a secure server so that it may be remotely assessed as needed via a secure website. In addition to automatically transmitting data for analysis, all data from the SWD 1000 monitor's removable storage will be extracted upon return of the equipment to ZOLL.

6.1.3 Subject Enrollment Data

General demographic and medical history information will be collected from subjects enrolled in the study (90D0119_CRF).

6.1.4 Therapy Contextual Information

In the unexpected event that a shock is delivered, anecdotal information may be collected from the patient and any witnesses. This information will be used to determine if the patient and other witnesses interacted with the device as instructed during the treatment sequence.

6.2 Data Evaluation

6.2.1 Safety Evaluation

The SWD 1000 safety endpoint will be evaluated based on signal quality. ECG quality relates to both safety (poor ECG quality may lead to inappropriate detections and/or shocks) and efficacy (poor ECG quality may interfere with the detection of a ventricular arrhythmia). The criteria for success are that 1) at least one lead is available for ECG monitoring (signal quality acceptable for algorithm input on one or more leads) for $\geq 98\%$ of the time the device is attached to the patient and 2) both leads are available for $\geq 95\%$ of the time the device is attached to the patient. The evaluation will be an average derived from all patients using the internal device flags regarding algorithm performance.

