3. STUDY OBJECTIVES

The objectives of this feasibility study focus on demonstrating that patients presenting to the ED following a cardiac or potentially cardiac syncopal event, i.e., undiagnosed in nature, may be managed as outpatients and protected from sudden cardiac death by equipping them with, and training them to use, the SWD 1000 prior to ED discharge. Capturing accurate data on patient and caregiver behavior is critically dependent on utilizing the device in a real-world clinical setting.

- 3.1 To observe the level of care provided to SWD 1000-equipped syncope patients on an outpatient basis.
- 3.2 To confirm that the SWD 1000 meets expected safety. Monitoring quality will be used as a surrogate for safety in this feasibility study. Specifically, on average monitoring will be inhibited by noise no greater than 2% of the time worn and monitoring using single lead analysis will be no greater than 5% of the time worn.

It is not anticipated that any treatable events will be observed during this testing period. However, should any events occur, it is expected that the device will yield results at least comparable to those obtained through experience with the currently-approved LifeVest wearable defibrillator.

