9. TRIAL DESIGN AND STUDY SIZE

The study is a single arm, open enrollment feasibility study. A maximum of twenty clinical sites will be used to enroll subjects. The multi-site approach is intended to increase variability in the observation of ED characteristics, such as differences in staffing, staff responsibilities, and patient demographic.

A minimum of 50 subjects and a maximum of 80 subjects will be enrolled. The sample size is based on the expected safety objective, which states:

"Specifically, on average monitoring will be inhibited by noise no greater than 2% of the time worn and monitoring using single lead analysis will be no greater than 5% of the time worn."

This objective was taken directly from the LifeVest System Input Requirements (90A0118):

"[R274] Monitoring shall be inhibited by noise no greater than 2% of the time worn on average within the intended patient populations. [R275] Monitoring using single lead analysis shall occur no greater than 5% of the time worn on average within the intended patient populations."

In 2012, the device records of approximately 14,000 patients who used the LifeVest 4000 system were analyzed to determine the system performance. The device records the time when the device is on, when

each of the two ECG channels is determined to be unsuitable for determining the presence of an arrhythmia, and when both leads are determined to be unsuitable. Using these, the time the device was unable to monitor (DUAL) and the time the device was using only a single lead for monitoring (SINGLE) was determined. Each patient's proportion of time spent in SINGLE or DUAL was calculated, then overall descriptive statistics were derived using Excel spreadsheet functions:

	SINGLE	DUAL
Mean	.040	.005
Standard Deviation	.051	.015
Median	.024	.002
Maximum	.762	.644
Minimum	.000	.000
Standard Error	.000431	.000127
95% lower bound	.039989	.004997
95% upper bound	.040011	.005003

The performance of the SWD 1000 is expected to be similar to the 4000 system. A confidence interval of 80% to 90% was used to define expectations of meeting the safety objective for the feasibility stage. A general formula for calculating sample size based on a confidence interval was used:

$$n = \left(2z_{\frac{\alpha}{2}}\sigma/L\right)^2$$

To calculate the sample size for SINGLE performance of the SWD 1000 against the 4000 system:

Confidence: 80%

$$z_{\frac{\alpha}{2}} = 1.28$$

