Allowable difference = 0.01 (0.05 permitted, 0.04 is current 4000 performance)

$$L = 0.02$$

Standard deviation = 0.051 (assumed to be similar to the 4000)

$$n = \left(2z_{\frac{\alpha}{2}}\sigma/L\right)^2 = 42$$

Confidence: 90%

$$z_{\frac{\alpha}{2}} = 1.645$$

Allowable difference = 0.01 (0.05 permitted, 0.04 is current 4000 performance)

$$L = .02$$

Standard deviation = 0.051 (assumed to be similar to the 4000)

$$n = \left(2z_{\frac{\alpha}{2}}\sigma/L\right)^2 = 71$$

To calculate the sample size for DUAL performance of the SWD 1000 against the 4000 system:

Confidence: 90%

$$z_{\frac{\alpha}{2}} = 1.645$$

Allowable difference = 0.01 (0.02 permitted, 0.005 is current 4000 performance)
 $L = 0.02$

Standard deviation = 0.015 (assumed to be similar to the 4000)
 $n = \frac{(2z_{\alpha/2}\sigma)^2}{L^2} = 7$

Thus, a sample size of 50 to 80 subjects is expected to demonstrate that both SINGLE and DUAL performance meet the safety objective of the feasibility study.

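### The safety success rule rests on an average with no interval reported, so it does not support the words confirm and demonstrate that the plan attaches to it

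*Combined protocol and SAP*

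**What the plan says.** Objective 3.2 is "To confirm that the SWD 1000 meets expected safety", with signal quality as a surrogate. It sets two limits. The first covers loss of monitoring: "on average monitoring will be inhibited by noise no greater than 2% of the time worn". The second covers reliance on one lead: "monitoring using single lead analysis will be no greater than 5% of the time worn".

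Section 6.2.1 turns these into formal criteria, beginning "The criteria for success are that 1) at least one lead is available for ECG monitoring" for at least 98% of attached time. The second criterion is both leads available for at least 95% of attached time. The decision statistic is then given: "The evaluation will be an average derived from all patients using the internal device flags regarding algorithm performance". No interval, confidence level or test is attached. Section 13 adds none for this endpoint; it lists the stored data and says results will be compared with commercial LifeVest use.

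Section 9 does use an interval, for sizing: "A confidence interval of 80% to 90% was used to define expectations of meeting the safety objective for the feasibility stage". It closes by saying that 50 to 80 subjects are expected to demonstrate that both SINGLE and DUAL meet the objective.

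**The concern.** The quoted device requirements in Section 9 concern the average within the intended patient populations. That is a population mean, which 50 to 80 subjects only estimate. Per-subject proportions vary widely: in the LifeVest 4000 records SINGLE has mean 0.040, SD 0.051, median 0.024 and maximum 0.762. An observed average below 5% can therefore come from a device whose true mean is above 5%, and a report without an interval would not show how plausible that is.

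Signal quality is the only safety measure with a success criterion. Section 10 treats similar ECG quality as reasonable assurance that the device will perform as expected. A statement that safety was confirmed would carry that weight into later studies without any stated sampling error.

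**Working it through.** **Inputs (Section 9).** SINGLE: "Standard deviation = 0.051 (assumed to be similar to the 4000"; "Allowable difference = 0.01 (0.05 permitted, 0.04 is current 4000 performance". DUAL: mean 0.005, SD 0.015, limit 0.02. n = 50 to 80.

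**The plan's own figures.** n = (2zσ/L)², with L = 0.02.
- SINGLE, 80%: (2 × 1.28 × 0.051/0.02)² = 42.6 (stated 42; 43 if rounded up).
- SINGLE, 90%: (2 × 1.645 × 0.051/0.02)² = 70.4 (stated 71).
- DUAL, 90%: (2 × 1.645 × 0.015/0.02)² = 6.1 (stated 7).

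The figures reproduce, apart from rounding in the first.

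**What that sizing delivers.** With L = 0.02 the formula is n = (zσ/0.01)². At that n, a device with true mean 0.04 has an observed mean at or below 0.05 with probability Φ(z): about 90% for z = 1.28 and 95% for z = 1.645. So the sizing does protect a device that performs as assumed.

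**Chance of passing the rule on the average, SINGLE limit 5%.** P(pass) = Φ((0.05 − μ)/SE), with SE = 0.051/√n, which is 0.00721 at n = 50 and 0.00570 at n = 80.

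| True mean μ | n = 50 | n = 80 |
|---|---|---|
| 4.0% | 92% | 96% |
| 5.5% | 24% | 19% |
| 6.0% | 8% | 4% |

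DUAL is not limiting at the assumed values: (0.02 − 0.005)/(0.015/√50) = 7.1 standard errors.

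**Skewness.** The shape is an assumption. A lognormal with mean 0.040 and SD 0.051 has median 0.0247, close to the stated 0.024. Holding its coefficient of variation at 0.051/0.040 = 1.275, 100,000 simulated trials per setting give a pass rate of about 33% (n = 50) and 27% (n = 80) at 5.5%, and about 17% and 10 to 11% at 6.0%.

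**If the upper limit also had to lie within 5%.** P = Φ((0.05 − μ)/SE − z). At μ = 0.04:
- 80% interval: 54% (n = 50) to 68% (n = 80). The observed mean must be at most 0.0408 or 0.0427.
- 90% interval: 40% to 54%. The observed mean must be at most 0.0381 or 0.0406.

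Under the same lognormal with true mean 5.0%, the upper limit of a normal-theory 90% interval falls within 5% about 12% to 14% of the time, and that of a percentile bootstrap about 11% to 13%. The nominal figure is 5%.

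**The two wordings of the second limit.** Requiring both leads for at least 95% of the time limits SINGLE + DUAL to 5%, whereas 3.2 and Section 9 limit SINGLE alone. On the reference means the sum is 0.040 + 0.005 = 0.045, leaving 0.005 of room rather than 0.010. If the sum also had SD 0.051 (an assumption), a device at the reference values would pass 6.2.1 with probability Φ(0.005/SE): 76% (n = 50) to 81% (n = 80).

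**The case against.** A reader might infer that Section 9 promised an interval as the decision rule and that 6.2.1 contradicts it. The text does not go that far. It says the interval was used to define expectations of meeting the objective, and the 92% to 96% pass rate at a true mean of 4% shows that the sizing and the rule on the average can stand together.

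A reader might also point out that a device exactly at 5.0% passes half the time and treat this as a false-pass rate. It is not one. The limit is no greater than 5%, so that device meets the requirement, and about one half at the threshold follows from any rule that compares an unbiased average with a limit. The relevant figures are those for true means above 5%.

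The remaining defence is that the requirement is itself an average, that this is a single-arm feasibility study, that the Protocol Summary leaves definitive safety and efficacy to later studies, and that formal error control is promised nowhere. This stands as a reason not to impose a strict test. It does not justify the words confirm and demonstrate, or leaving the interval out of the report.

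**Conclusion.** The concern holds in a limited form. The average is a defensible feasibility criterion, and the sample size suits it as far as passing a good device goes. The plan does not control, or report, the uncertainty that matters for passing a bad one: 24% to 19% at a true SINGLE mean of 5.5%, and 8% to 4% at 6.0%, with higher rates if the data are as skewed as the reference summary suggests.

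These figures assume that the SD of 0.051 from LifeVest 4000 records carries over to the SWD 1000 (for the normal figures, at every true mean), that the average is an unweighted mean of per-subject proportions as in Section 9, that DUAL is comfortably met, and that the limit is on SINGLE alone. Under the wording of criterion 2 in 6.2.1 they would apply to the sum SINGLE + DUAL, given an SD of 0.051 for the sum.

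This should be fixed. It affects what the report may claim, not whether the study can run.

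**What to change.** 1. Reconcile criterion 2 of 6.2.1 with 3.2 and Section 9: state whether the 5% limit applies to SINGLE or to SINGLE plus DUAL.
2. Keep the average as the feasibility criterion. In 6.2.1 and Section 13, pre-specify that each average is reported with its two-sided 80% and 90% intervals (the levels in Section 9), by a method suited to skewed per-subject proportions, with its actual error rate checked by simulation.
3. Fix the wording of the conclusion in advance. If only the average is within the limit, report that the average met the requirement. Use confirm or demonstrate only when the upper limit is also within the bound, and state beforehand which level governs. Align 3.2 and the last sentence of Section 9 with this.

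The cost is protocol wording and a little analysis code, with no new subjects or data. The downside should be stated in the plan. A device at the assumed 4% would earn the stronger wording only 54% to 68% (80% interval) or 40% to 54% (90% interval) of the time, and on skewed data neither interval method checked fully reaches its nominal error rate. Making the upper limit the success criterion itself would be a different design: 80% power at a true mean of 4% would need about (0.051 × (1.282 + 0.842)/0.01)² ≈ 118 subjects with the 80% interval, or (0.051 × (1.645 + 0.842)/0.01)² ≈ 161 with the 90% interval. That is not proposed here.
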